6.5 Investigational Product Accountability and Compliance

6.5.1 Dispensing Investigational Product

From Day-2 onwards during the confinement period, each mCC will be dispensed to the subjects one by one. Subjects in the THS 2.2 Menthol arm will be provided by the site study collaborators with Menthol Tobacco Sticks from Day 1 to Day 5 stick by stick. One mCC/Menthol Tobacco Stick will be allowed at a time, as per the study design, and documented in an appropriate Log.

On each day of the confinement period, the time of dispense and return for each product has to be documented from Day-1 for CC and from Day 1 for Menthol Tobacco Sticks onwards. The start of product use will correspond to the time of dispense of the first mCC/Menthol Tobacco Stick. The subject must not take a puff of the Menthol Tobacco Stick during the

pre-heating time. The product will not be promoted for commercial distribution or test market.

During the ambulatory period, subjects in the THS 2.2 Menthol arm will be provided with an anticipated amount of Menthol Tobacco Sticks to cover the period until the next study visit. An additional number of Menthol Tobacco sticks will be dispensed to the subjects at these visits to cover for any unexpected delay to the visit schedule made by the subject. Extra delivery of THS Menthol Tobacco Sticks in between two visits may be envisaged. Subjects in the mCC arm and will buy their mCCs directly from shops.

6.5.2 Storage and Accountability

The study collaborator (the IP product storage manager) designated by the head of the investigational site will be responsible for the storage and accountability of the IPs in accordance to sponsor's requirements.

The THS 2.2 Menthol and mCC will be stored in a secured storage site with access limited to authorized personnel only. Full accountability of the distributed products will be ensured by designated IP storage manager.

6.5.2.1 Confinement Period

On each day of the confinement period, study collaborators will record on the Accountability Log every occasion from Day -1 to time of Discharge on Day 6 that mCCs are dispensed to a subject by the study collaborator and every occasion from Day 1 to time of Discharge on Day 6 that the THS 2.2 Menthol product components (i.e. THS Tobacco Stick holder, THS charging unit, THS accessories) and Menthol Tobacco Sticks are dispensed to a subject.

Subjects will return each butt of mCC immediately after use from Day -1 to Day 6 for accountability. This will be documented in appropriate log.

Immediately after use, all tobacco plugs of all used Menthol Tobacco Sticks will be separated from the filters and the tobacco plugs and the filters will be collected from Day 1 to Day 5, using dedicated vials for accountability and subsequent analysis of potential combustion occurrences and nicotine retained in the filters (see also Section 7.8.2). This will be documented in an appropriate log.

6.5.2.2 Ambulatory Period

THS 2.2 Arm:

Subjects must return any empty packs and partially used packs of Menthol Tobacco Sticks they have used during the preceding weeks to the site for accountability. After accountability they will be destroyed at study completion in accordance with sponsor's requirements.

All tobacco plugs from Menthol Tobacco Sticks used after check-in to the investigational site until 11:00 PM on Day 30, Day 60, and Day 90 will be collected in dedicated vials for subsequent analysis of potential combustion occurrences. No filter analysis of the Menthol Tobacco Sticks will be conducted during the visits of the ambulatory period.

mConventional Cigarettes Arm:

No IP accountability will be done for mCC.

Smoking Abstinence Arm:

No IP accountability will be done for SA arm.

6.5.3 Investigational Product Retention

The study site will destroy or return to the Sponsor any unused Menthol Tobacco Sticks and will return to the Sponsor the THS 2.2 Menthol product components upon study completion. Retention of THS 2.2 Menthol products will be documented.

Irrespective of the study arm on the time of Discharge from the clinic, the study collaborators will return to the subjects any remaining mCCs given to them on the day of Admission.

6.5.4 Compliance to Investigational Product

During the confinement period, compliance for all study arms will be ensured by strict dispensation of the products (product by product) and collection of used Menthol Tobacco Sticks/CC butts will be documented in appropriate log..

During the ambulatory period, subjects in the 3 study arms will capture, from the time of Discharge on Day 6 to Day 90 11:00 PM the number of product used (e.g., menthol and non-menthol CC, Menthol Tobacco Sticks, or any other tobacco /nicotine-containing products including NRT) on a daily basis in the product use electronic diary. The product use electronic diary will be supplied by Sponsor and distributed to the subjects by the study site collaborator. The product use electronic diary will serve as a compliance tool in the three arms. On Day 6, the compliance to the product will be ensured by the merge of the

accountability log (from 06:30 AM to time of discharge) and the product use electronic diary. In case of discrepancy between the log and the electronic diary entries, the electronic diary entries will be considered as source of data.

In addition, in the SA arm, compliance will be chemically verified using an exhaled CO breath test during both the confinement and ambulatory periods. The cut-off point for the CO breath test value to distinguish mCC use versus no mCC use will be 10 ppm (Benowitz et al., 2002).

6.6 Restrictions

6.6.1 Smoking Restrictions and Restrictions to the Smoking Abstinence Arm

6.6.1.1 Confinement Period

To avoid smoke cross contamination between the three study arms, subjects in the THS 2.2 Menthol and the mCC arm must smoke in separate rooms and subjects allocated to the SA arm should not have access to the smoking rooms. All precautions should be taken to remove any temptation to smoke for subjects who are randomized to the SA arm.

In the THS 2.2 Menthol and SA arms, subjects will not be allowed to smoke any mCC or use any nicotine/tobacco-containing products (including NRT) from Day 1 (06:30 AM) until the time of Discharge on Day 6. In the mCC arm, subjects will not be allowed to use the THS 2.2 Menthol, any nicotine/tobacco containing products other than mCC brought to the site by the subject to the site. In the SA arm, intensive support including psychological support will be provided upon the request of the subject or of the Investigator or study site collaborator.

Smoking will generally only be allowed during the designated smoking times, from 06:30 AM to 11:00 PM. Smokers will not have free access to their mCC or THS 2.2 Menthol; these will be dispensed by the study collaborator individually as described in Section 6.5.1.

From admission on site, smoking will not be allowed during assessments on the Admission Day at the discretion of the site. Smoking will be allowed on Day 6 after CYP2A6 activity measurements, assessment of cough and MNWS questionnaire completion and spirometry, have been conducted.

In general, the performance of scheduled procedures has priority over the wish of a subject to use the product. However, this is different at Day 5 due to the assessment of the nicotine profile. If the subject wants to use the product at Day 5 around the time of the blood draw, he/she should use the product first and the blood will be drawn after product use.

6.6.1.2 Ambulatory Period

Subjects in the THS 2.2 Menthol arm will be instructed to exclusively use THS 2.2 Menthol and subjects in the SA arm will be instructed to remain abstinent from smoking with or without NRT. Subjects in the SA arm may use NRT if considered necessary by the Investigator or if requested by the subject. NRT products will be used as per the product label, and may be purchased by subjects at a pharmacy. Subjects will be reimbursed. Intensive support including psychological support will be provided upon the request of the subject or of the Investigator or study collaborator.

Product use will be allowed during the ambulatory visits from 08:00 AM to 11:00 PM on Day 30 and Day 60, and on Day 90. On Day 31, and Day 61, product use will be allowed from 06:30 AM. However, in the morning of Day 91, smoking will not be allowed until assessment of cough and MNWS questionnaires completion and CYP2A6 and spirometry, have been performed on site.

6.6.2 Dietary Restrictions

6.6.2.1 Confinement Period

A standard diet will be designed by a dietician. For each meal, the caloric and fat content should be controlled in order to avoid “high-fat” diet. The FDA guidance on food-effect studies for bioequivalency testing identifies a “high-fat” diet as a diet which maintains approximatively 50 percent of total caloric content of the meal and is high in calories (approximately 800 to 1000 calories) (FDA, 2002).

In order to avoid any effect on assessment of BoExp, grilled or pan-fried meat, smoked pre-cooked meats (e.g., tuna, ham, corned beef, and meats), smoked bacon and sausage will not be permitted (Tiffany et al., 1991). In addition, to avoid any effect on the measurement of CYP1A2 activity, alcohol, broccoli, brussels sprouts, cauliflower, grapefruit, and xanthine-containing foods and beverages (coffee, tea, chocolate, cocoa, mate, guarana etc.) will be forbidden (Faber et al., 2004) (except for the intake of the caffeine tablet for CYP1A2 measurement). Consumption of quinine-containing drinks (e.g., tonic water) is not allowed.

Subjects are not allowed to bring their own food or beverages to the investigational site. Meals will be served according to the schedules provided in Section 9. Additional light snack, fruits, and raw vegetables can be distributed to the subjects without restrictions at any time during confinement as long as they fulfill the above requirements described in this section. Consumption of water is allowed as desired. The same menu and meal schedule will be administered uniformly for all subjects in all study arms. In addition for the purpose of the Ames test planned on Day 0 and Day 5, the menus served on Day-1 and Day 4 will be identical.

Fasting state has to be observed for at least 10 hours prior to blood draws for:

1. safety laboratory on screening, Day 0, Day 6
2. risk marker in serum/plasma/blood on Day 0 and Day 6.
3. serum/plasma bio-banking samples for further analysis of BoExp and risk markers at the Screening Visit, on Day 0, Day 6.
4. blood bio-banking for transcriptomics on Day 0, Day 6.

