7.5.2.4 Ames Mutagenicity Test

Urine mutagenicity, a biomarker for measuring mutagen load, will be measured on Day 0, Day 5 and on Day 90 Visit in 24-hour urine. The urinary determination of each sample will be done in one bacterial strain (*S. typhimurium* strain YG1024), using S9 metabolic activation and 4 doses for each of the urine extracts.

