7.7.2 Urine samples

Spot urine samples will be used for the urine drug screen, urine cotinine screen, urine pregnancy test, and safety urinalysis.

24-hour urine collection during the confinement period:

For the 24-hour urine collection, subjects will empty their bladders shortly before 06:30 AM on the study day indicated in the Schedule of Events (Appendix 1). The collection period starts at 06:30 AM and ends on the following day at 06:29 AM. Shortly before 06:29 AM, after nearly 24-hours of urine collection, subjects will empty their bladder again and this urine will be used as the final portion of the 24-hour urine sample.

At time of Discharge on Day 6, subjects will empty their bladder shortly before 06:29. This will be the last urine portion for the 24-hour urine for the Day 5 dot mark in the Schedule of Events.

24-hour urine collection during the ambulatory period:

Twenty four-hour urine fraction will be collected on Day 30 Visit, Day 60 Visit, and Day 90 Visit) at site.

Subject will be asked to come at site at around 08:00 AM on Day 30, Day 60 and Day 90 and will remain overnight on site until respectively Day 31, Day 61, and Day 91. Subject will be asked to empty his bladder on Day 30, Day 60, and Day 90 shortly before 09:00 AM minutes (this urine will be discarded). Then collection period will start at 09:00 AM \pm 20 minutes. After nearly 24-hours of urine collection the day later at 08:59 AM \pm 20 minutes, subjects will empty their bladder again and this urine will be used as the final portion of the 24-hour urine sample.

For both confinement and ambulatory periods;

All urine passed during the sampling period must be collected and put into the sampling bottle, with the exception of about 10 mL for the spot urine tests (described above). No urine

must be passed into the toilet. The volume of 24-hour urine, the start and the end time of urine collection will be recorded by the study collaborators.

For assessment of urine BoExp, creatinine for normalization of urine BoExp, 8-epi-PGF2 α and 11-TBX-B2, sample bio-banking and urine mutagenicity, aliquots from the 24-hour urine collection will be taken. In the Schedule of Events for the 24-hour urine collection (see Appendix 1), the dot corresponds to the day on which the 24-hour urine collection period starts. For example, for NEQ measured at Day 30 Visit in the 24-hour urine collection that starts on Day 30 and ends later on Day 31.

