t: cough questionnaire to be done daily from Day 0 to Day 6 prior product use but no later than 10:00 AM and at every visit during the ambulatory period no later than 10:00 AM, i.e. Day 30 Visit (Day 31), and Day 60 Visit (Day 61) irrespective of time of product use and Day 90 Visit (Day 91) prior to smoking.

u: Samples will only be taken if additional consent for bio-banking is given by the subject.

v: Spontaneous reporting of new AEs/SAEs by the subject and active follow-up of ongoing AEs/SAEs by the site.

**Table A2 Schedule for 24 hour Urine Collection Assessments****During the confinement and ambulatory periods, the dot corresponds to the start of 24-hour urine collection.**

	Baseline period		Confinement Exposure Period 24-hour urine						Ambulatory Exposure Period 24-hour-urine		
			Day -1 to Day 0	Day 0 to Day 1	Day 1 to Day 2	Day 2 to Day 3	Day 3 to Day 4	Day 4 to Day 5	Day 5 to Day 6	Day 30 to Day 31	Day 60 to Day 61
BoExp in urine ^a	●	●	●	●	●	●	●	●	●	●	●
Creatinine	●	●	●	●	●	●	●	●	●	●	●
11-DTX-B2 and 8-epi-PGF2 α		●						●	●	●	●
Ames mutagenicity test		●						●			●
Bio-banking ^b		●						●			●

Abbreviations: Abbreviations: 8-epi-PGF2 α = 8-epi-prostaglandine F2 α ; 11-DTX-B2 = 11-dehydro-thromboxane B2^a MHBMA, 3-HPMA, S-PMA, total NNAL, 1-OHP, total NNN, 4-ABP, 1-NA, 2-NA, o-tol, CEMA, HEMA, 3-hydroxybenzo(a)pyrene, HMPMA, S-BMA, NEQ.

b: Samples will only be taken if additional consent for BoExp bio-banking is given by the subject.

During the confinement and ambulatory periods, when the BoExp is mentioned to be assessed at Day x, it corresponds to the start of urine collection, For example, for NEQ assessed on Day 5, it will be the measurement of NEQ in the Day 5-Day 6 24-hour urine collection.

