12.6.3.6 Ames Mutagenicity Test

The 24 hour urine collection for the Ames mutagenicity test will be on Day 0, Day 5 and Day 90.

Descriptive statistics of the values and percent changes on Day 5 and Day 90 from Baseline of the YG1024+S9 mutagenicity will be provided, along with listings.

All summaries will be performed on the FAS, and PP Set.

The data will be presented in the below outputs:

TFL number	Title
TABLES	
15.2.4.46.1	Descriptive Statistics of Ames Mutagenicity Test (YG1024+S9) (units) – PP Set
15.2.4.46.2	Descriptive Statistics of Ames Mutagenicity Test (YG1024+S9) (units) – FAS
LISTINGS	
15.3.5.1	Listing of Mutagenicity Results

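### The identical-menu rule for the Ames test covers the day before each urine collection, so the meals eaten during the Day 0 and Day 5 collections need not match

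*Protocol*

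**What the plan says.** Protocol 6.6.2.1 sets a dietician-designed diet for confinement. It excludes grilled, pan-fried and smoked meats, bars subjects' own food, and gives every arm the same menu and meal times. As a further measure, and naming the Ames test on Day 0 and Day 5 as the purpose, it adds that "the menus served on Day-1 and Day 4 will be identical".

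Protocol 7.5.2.4 says that mutagenicity "will be measured on Day 0, Day 5 and on Day 90 Visit in 24-hour urine". SAP 12.6.3.6 agrees: "The 24 hour urine collection for the Ames mutagenicity test will be on Day 0, Day 5 and Day 90".

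The meaning of Day 0 and Day 5 urine is fixed elsewhere. Protocol 7.7.2 says of a confinement collection: "The collection period starts at 06:30 AM and ends on the following day at 06:29 AM". It adds that in the Schedule of Events "the dot corresponds to the day on which the 24-hour urine collection period starts". The note to Table A2 in Appendix 1 repeats that "when the BoExp is mentioned to be assessed at Day x, it corresponds to the start of urine collection", and SAP 12.1.4 uses the same convention.

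The planned output in SAP 12.6.3.6 is: "Descriptive statistics of the values and percent changes on Day 5 and Day 90 from Baseline of the YG1024+S9 mutagenicity will be provided". No model or test is planned for this endpoint.

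**The concern.** The protocol treats diet as able to affect this assay enough to justify matching menus between time points, over and above the general diet rules. The matching then applies to days on which no Ames urine is collected. Breakfast, lunch, snacks and dinner inside the two Ames windows are Day 0 and Day 5 meals, and no section asks for those to be the same.

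At stake is the within-arm percent change from baseline to Day 5. If the two menus happened to carry different mutagen loads, the change in any arm, including the mCC and SA reference arms, would combine the effect of the assigned product or regimen with an effect of the food.

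**Working it through.** The plan gives no figure for this point. The check compares dates and clock times, followed by simple algebra on which contrasts a menu effect could reach.

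**1. Which bottle carries the Ames test** (Protocol Section 9, Tables 10, 11, 15 and 16)

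| Bottle | Window | Closed on | Ames aliquot? | Meals in window | Menu matched? |
|---|---|---|---|---|---|
| Day -1 | Day -1 06:30 to Day 0 06:29 | Day 0 (Table 10) | No | Day -1 | Yes |
| Day 0 | Day 0 06:30 to Day 1 06:29 | Day 1 (Table 11) | Yes | Day 0 | Not required |
| Day 4 | Day 4 06:30 to Day 5 06:29 | Day 5 (Table 15) | No | Day 4 | Yes |
| Day 5 | Day 5 06:30 to Day 6 06:29 | Day 6 (Table 16) | Yes | Day 5 | Not required |

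The matched menus coincide with two collections in which mutagenicity is not measured. The offset is one day at both time points, and no matched-menu meal falls inside an Ames window. The rule would fit only if Day 0 and Day 5 meant the collections that end on those days, which contradicts Protocol 7.7.2, the Table A2 note and SAP 12.1.4.

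**2. Gap between the last matched meal and the Ames window.** Day -1 dinner is over by 21:00 (Table 9) and the Day 0 collection opens at 06:30. The gap is 3 h to midnight + 6.5 h = 9.5 h. The bladder is emptied into the earlier bottle just before the new one starts.

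**3. What a menu effect could bias.** The documents give no size for such an effect, so the values here are assumptions.

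- *Multiplicative effect.* Let m be the Day 5/Day 0 menu factor, assumed to lie between 0.80 and 1.25. An arm with no true change shows m - 1, that is 0.80 - 1 = -20% to 1.25 - 1 = +25%. For two arms with true Day 5/Day 0 ratios r1 and r2, the ratio of changes is (r1 × m)/(r2 × m) = r1/r2, so m cancels.
- *Additive effect.* Assume a baseline of 100 in both arms, true Day 5 levels of 100 (mCC) and 30 (THS 2.2 Menthol), and 20 units from diet in each. If the Day 5 menu doubles the diet part, the Day 5 levels become 120 and 50. The within-arm changes move from 0 to +20 (mCC) and from -70 to -50 (THS 2.2 Menthol). The difference of changes stays at -70. The ratio of Day 5 levels does not stay fixed: the apparent reduction against mCC moves from 1 - 30/100 = 70% to 1 - 50/120 = 58%.

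A shared menu effect therefore reaches the within-arm change in either case. An additive effect drops out of the difference of changes, and a multiplicative effect drops out of the ratio.

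**The case against.** The strongest case on the other side has four parts.

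- **Not required is not the same as different.** A reader might infer that the Day 0 and Day 5 menus were unequal and that the Ames result is confounded by diet. The documents do not support that. They are silent on those two menus, which may have been the same or nearly so. This part stands.
- **Other diet controls apply every day.** The standard diet and the exclusion of grilled, pan-fried and smoked meats hold on Day 0 and Day 5 too, which limits how far two menus could differ. This stands, although the protocol itself thought menu matching worth adding to those controls.
- **The objective compares arms.** Protocol 3.3 describes mutagenicity in switchers against continuing mCC smokers and SA. With one menu for all arms, the mCC arm would reveal a menu shift and the between-arm difference of changes is protected. This stands, apart from the light snacks, fruit and raw vegetables allowed without restriction. It does not protect a within-arm percent change read on its own, which is the summary that SAP 12.6.3.6 specifies.
- **Matching the day before may be deliberate.** It could equalise carry-over into a collection that opens at 06:30. That is possible, and it is a reason to keep the existing rule. But the protocol gives no such rationale, and carry-over control would still leave the food eaten during the collection unmatched.

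**Conclusion.** The identical-menu days fall one day before the Ames collections by the documents' own labelling, and matching is not required for the meals eaten during either confinement collection. The consequence is narrow: the within-arm percent change from baseline to Day 5 is open to a menu effect whose size cannot be derived from the documents. The -20% to +25% range rests wholly on the assumed factor of 0.80 to 1.25.

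Two stronger readings should be resisted. The documents do not show that the menus differed, and they do not show that the comparison between arms is biased, because the confinement menu is common to all arms. The endpoint is exploratory and summarised descriptively. The five primary endpoints, the success criterion and the sample size are untouched.

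The Day 90 Ames urine has a related limit. Protocol 6.6.2.2 lifts the confinement diet rules for the ambulatory period, so that collection has no menu matching at all. Its percent change from baseline should likewise be read only relative to the other arms.

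**What to change.** Amend Protocol 6.6.2.1 to require identical menus on Day 0 and Day 5, and keep Day -1 and Day 4 matched so that carry-over from the previous day is also equal. State the reason for each pair. The cost is about one sentence and some menu planning, since the site already supplies a standard diet.

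If confinement is already complete, which is plausible because SAP Section 8 already reports the number randomised, two steps remain. Report the menus actually served on Day 0 and Day 5. Add to SAP 12.6.3.6 that the Day 5 percent change is to be interpreted relative to the mCC and SA arms, and that the Day 90 change is to be read the same way because no menu matching applies there. This needs no new data beyond the site's menu records.

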6.6.2.2 Ambulatory Period

The above dietary restrictions are not applicable for the ambulatory period. However, 3 days prior to the Day 30 Visit, the Day 60 Visit, and the Day 90 Visit, and during visits on site, subjects will be asked by the study collaborators to refrain from consuming grapefruit or grapefruit-containing products, or quinine-containing drinks (e.g., tonic water). Alcohol, broccoli, brussels sprouts, cauliflower, chargrilled meat, xanthine-containing foods and beverages (e.g., coffee, tea, chocolate, cocoa, mate, guarana) will not be allowed on site during the ambulatory visits.

A fasting state has to be observed for at least 10 hours prior to blood draws for:

1. safety laboratory on Day 31, Day 61, and Day 91
2. risk factor assessments in serum/plasma/blood on Day 31, Day 61 and Day 91.
3. serum/plasma bio-banking samples for further analysis of BoExp and risk markers on Day 91.
4. blood bio-banking for transcriptomics on Day 91.

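### The confinement meat ban, imposed to protect the biomarkers of exposure, is mostly lifted at the Day 30, 60 and 90 visits, so Day 90 secondary biomarkers and the Ames test may carry an uncontrolled dietary contribution

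*Protocol*

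**What the plan says.** In confinement (Protocol 6.6.2.1) the purpose of the meat rule is explicit: "In order to avoid any effect on assessment of BoExp". The rule itself is that "grilled or pan-fried meat, smoked pre-cooked meats (e.g., tuna, ham, corned beef, and meats), smoked bacon and sausage will not be permitted". The same section requires one menu for all arms and, for the Ames test, that "the menus served on Day-1 and Day 4 will be identical".

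For the ambulatory period (Protocol 6.6.2.2) the rule changes: "The above dietary restrictions are not applicable for the ambulatory period". For the three days before each visit and during it, subjects are asked to avoid only grapefruit products and quinine drinks. The on-site list contains a single meat item: "chargrilled meat, xanthine-containing foods and beverages (e.g., coffee, tea, chocolate, cocoa, mate, guarana) will not be allowed on site during the ambulatory visits".

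No other passage restores the wider list. The visit schedules for Days 30, 60 and 90 (Protocol 9.3, Tables 17 and 18) show when meals are taken but not what may be served. The SAP has no dietary rule and no adjustment for diet.

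**The concern.** The protocol gives its own reason for the ban, namely that these meats could disturb BoExp assessment. That reason does not lapse when subjects return for a supervised 24-hour urine collection. Yet at those visits pan-fried and smoked meats are unrestricted, even in meals the site controls.

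Three sets of results are exposed:

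- **Secondary BoExp at Day 90.** Their statistical significance is evaluated when Day 5 is significant (Protocol 12.6.4; SAP 12.6.2.1), and they are also compared with SA.
- **MHBMA, 3-HPMA and S-PMA at Day 90.** These Day 5 primary markers are analysed again as secondary analyses, again with a comparison against SA (SAP 12.6.2).
- **The Ames test at Day 90.** It is summarised with percent change from baseline (SAP 12.6.3.6), but the menu matching set for confinement has no Day 90 counterpart.

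Baseline values come from the diet-controlled confinement stay. Percent change from baseline at Day 90 therefore compares two different dietary conditions.

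**Working it through.** The plan gives no figure for a dietary effect, so there is nothing to reproduce. The check compares the two sections and then works out the direction of any effect.

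**1. The two rules side by side**

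| Item | Confinement, including baseline and Day 5 (6.6.2.1) | Day 30, 60 and 90 visits (6.6.2.2) |
|---|---|---|
| Grilled meat | Barred | Only chargrilled, only on site |
| Pan-fried meat | Barred | No rule |
| Smoked pre-cooked meats, smoked bacon, sausage | Barred | No rule |
| Menu | Same for all arms; Day -1 and Day 4 matched | No rule |

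**2. Timing.** Ambulatory urine collection runs from about 09:00 AM to 08:59 AM the next day (Protocol 7.7.2; SAP Table 18). In Tables 17 and 18 lunch (before 02:30 PM) and dinner (before 09:00 PM) fall inside that window, and the first breakfast is close to its start. The meals that matter most are under site control.

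**3. Direction.** Set the mCC level to 1, THS to r and SA to s, and add the same background b to every arm.

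- THS:mCC becomes (r + b)/(1 + b). This exceeds r by b(1 − r)/(1 + b), which is positive when r < 1, so the ratio moves towards 1.
- THS:SA becomes (r + b)/(s + b). This falls below r/s by b(r − s)/[s(s + b)], which is positive when r > s, so THS looks closer to abstinence.

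An example shows that the two comparisons move in opposite senses for interpretation. Protocol Table 19 expects 3-HPMA ratios of 0.30 (THS/mCC) and 1.70 (THS/SA) on Day 5, so s = 0.30/1.70 = 0.176. The values of b are arbitrary assumptions, and carrying the Table 19 ratios to Day 90 is another.

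| Assumed b (fraction of mCC level) | THS:mCC | THS:SA |
|---|---|---|
| 0 | 0.30 | 1.70 |
| 0.05 | 0.35/1.05 = 0.33 | 0.35/0.226 = 1.55 |
| 0.10 | 0.40/1.10 = 0.36 | 0.40/0.276 = 1.45 |

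Nothing in the documents bounds b, and nothing says 3-HPMA is sensitive to diet. The table shows direction only and is not an estimate of size.

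**4. What an on-site rule can achieve.** Protocol 4.2 gives the Day 5 primary BoExp an average half-life of 24 hours or less. Assume first-order elimination and a meal eaten 12 hours before collection starts. The share of its excretion that falls in the 24-hour urine is 2^(−12/t) − 2^(−36/t):

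- t = 12 h: 0.500 − 0.125 = 0.375
- t = 24 h: 0.707 − 0.354 = about 0.35

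An on-site rule removes what is eaten during collection but not all earlier intake.

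**The case against.** The strongest reply is that the contrast is deliberate. Protocol 4.2 presents confinement as the tightly controlled setting and the ambulatory period as a view of real-world use, and looser diet control fits that. This stands in part. However, the rationale there concerns product use, not meals served on site during a supervised collection. Section 6.6.2.2 also still bars chargrilled meat on site, so meat was not regarded as irrelevant.

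The remaining objections limit how far the point can go, and they stand. A reader might infer any of the following, and the documents do not support them:

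- **That Day 90 markers do carry a dietary background.** The protocol permits these meats by silence; it does not prescribe them, and no visit menu is given.
- **That total 1-OHP or 3-hydroxybenzo(a)pyrene in particular is distorted.** The protocol speaks of BoExp in general, and the source it cites for the meat rule is a paper on a smoking-urges questionnaire.
- **That the primary result is compromised.** Four primary endpoints are measured on Day 5 under the controlled diet. The fifth, Total NNAL at Day 90, is described in Protocol 4.2 as specific to tobacco.
- **That the arms are treated differently.** The rule is the same in all arms, and the comparison is randomised and concurrent.
- **That a planned test of fading effect is biased.** Analyses over time are descriptive (Protocol 12.1.3), each Day 90 BoExp analysis compares arms at that visit, and the Ames test is descriptive only. Dual use is an expected reason for change after discharge, so diet could not be singled out.

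**Conclusion.** The point holds as a minor inconsistency. The protocol identifies a class of foods as a threat to BoExp assessment and then leaves most of that class unrestricted during the Day 30, 60 and 90 urine collections. The Day 90 secondary BoExp, the Day 90 repeat of MHBMA, 3-HPMA and S-PMA, and the Day 90 Ames test may therefore carry a dietary contribution that is controlled at baseline and Day 5.

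Its size cannot be stated from the documents. If the contribution is additive and shared across arms, it works against THS in the comparison with mCC, so a reduction shown there is not exaggerated by it. It works in favour of THS in the comparison with SA, which Protocol 4.2 uses as the reference for the largest achievable reduction. It also blurs descriptive change from baseline and from Day 5 to Day 90. The conclusion rests on the protocol's own premise that these meats matter, for which the documents offer no evidence.

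**What to change.** Reconcile Protocol 6.6.2.1 and 6.6.2.2 by applying the confinement meat list to meals served on site at the Day 30, 60 and 90 visits. The cost is a sentence in 6.6.2.2 and a menu change at three visits.

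A meat restriction in the days before each visit is not proposed. It could not be verified, because the electronic diary records only tobacco and nicotine use, and the protocol sets no such rule before admission to confinement.

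The study was expected to end on 31 August 2014 and SAP version 2.0 is dated 07 Nov 2014, so conduct is probably complete. In that case, add a short statement to the SAP or clinical study report beside the Day 90 secondary BoExp and Ames results. It should say that diet was not controlled as at baseline and Day 5, and that descriptive change from Day 5 to Day 90 and closeness of THS to SA at Day 90 should be read with that in mind. This costs one or two sentences and changes no analysis.
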